7.10. Safety Analysis

The analyses of safety will be performed on the Safety Analysis Set. The summary and display of TEAEs will be performed for the following data sets:

- (i) Part 1 data for the subjects who received blinded pexidartinib in Part 1;
- (ii) Part 1 data for the subjects who received blinded placebo in Part 1;

- (iii) All data from open-label pexidartinib treatment, ie, Part 2 data from all subjects;
- (iv) Aggregate pexidartinib data, ie, data from Parts 1 and 2 for the subjects who received pexidartinib in Parts 1 and 2 plus Part 2 data for the subjects who received blinded placebo in Part 1.

Terminology from version 19.1 of the Medical Dictionary for Drug Regulatory Activities (MedDRA) will be used to assign System Organ Class (SOC) and preferred term (PT) classification to AEs and diseases, based on the original terms entered on the eCRF.

The incidence of TEAEs will be summarized by SOC, PT, relationship to the study treatment, and severity for each treatment group. A by-subject listing will be provided for those subjects who experience an SAE, including death, or experience an AE associated with early withdrawal from the study or study treatment.

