2. Subjects on placebo in Part 1 are no longer allowed to enter Part 2 to receive open-label pexidartinib. After completion of the end of Part 1 assessments (Part 1 Completion visit/Early Termination visit), subjects who wish to continue onto the open label part of this study (Part 2) will be unblinded and those on placebo will be discontinued; subjects on pexidartinib in Part 1 may continue into Part 2 to continue to receive pexidartinib.
3. Investigators and subjects must be informed of the new safety information and decide whether to continue in the study. If, after consultation with the subject, it is deemed to be in their best interest to continue treatment, the subject must be re-consented.
4. The frequency of liver function testing is increased, and gamma-glutamyl transpeptidase (GGT) is added to the laboratory panel.

Updated hepatic safety risk information as of December 2017; please consult the IB for more information. Hepatotoxicity is an important adverse drug reaction. Elevations of liver transaminases and bilirubin have been observed in studies with pexidartinib, together with cases of drug-induced cholestasis. Cases of cholestasis have been observed in the first 8 weeks and have generally resolved with treatment discontinuation; however, some cases have been severe, with a protracted course requiring liver dialysis and, in 1 case, transplantation. Hepatotoxicity may be fatal. One fatal case with ongoing cholestatic liver injury at the time of death has been reported. Monitor patients closely as defined in the protocol. Protocol-defined dose reductions and discontinuations of pexidartinib, increased frequency of laboratory monitoring, and reporting of findings should be followed. In addition, rechallenge with pexidartinib should not be attempted without prior discussion with the Sponsor's Medical Monitor.

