3. STUDY DESIGN

3.1. Overall Plan

[figure not shown]
This trial is a two-part multi-center Phase 3 study in subjects with symptomatic PVNS or GCT-TS for whom surgical resection would be associated with potentially worsening functional limitation or severe morbidity (locally advanced disease). In Part 1, the double-blind phase, eligible candidates will be centrally randomized in a 1:1 ratio to receive either pexidartinib or placebo for 24 weeks. Randomization will be stratified by US versus non-US sites and by upper extremity versus lower extremity involvement.

Study treatment will be administered twice a day, every day. For the first 2 weeks in Part 1, subjects will take two capsules in the morning and three capsules in the evening, 1000 mg/d pexidartinib or matching placebo. Thereafter, dosing will be reduced to two capsules in the morning and two capsules in the evening, 800 mg/d pexidartinib or matching placebo. Subjects who had a dose reduction during the first 2 weeks will continue treatment at their reduced dose. Each treatment cycle will be 28 days in duration and subjects will be treated for up to 6 Cycles. Dose reductions, interruptions, and re-escalations after previous reductions for toxicity are permitted according to pre-specified guidelines. Those subjects who complete Part 1 (ie, complete 24 weeks of dosing and the Week 25 assessments) will be eligible to advance to Part 2, a long-term treatment phase where all subjects will take up to four capsules per day (800 mg/d) of open-label pexidartinib. Effective 30 Sep 2016, subjects on placebo are no longer allowed into Part 2 to receive open-label pexidartinib.

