7.10.1. Analysis of Treatment-emergent Adverse Events

TEAEs are AEs that occur, having been absent before the first dose of study treatment, or have worsened in severity after the initiating the study treatment. TEAEs will be coded using MedDRA and assigned grades based on version 4.0 of the National Cancer Institute's Common Terminology Criteria for Adverse Events (NCI CTCAE). The number and percentage of subjects reporting TEAEs will be tabulated by the worst CTCAE grade, SOC, and PT, with a breakdown by data set (Section 7.10). Similarly, the number and percentage of subjects reporting treatment-emergent SAEs will be tabulated, as well as TEAEs leading to discontinuation of study treatments.

A by-subject AE (including treatment-emergent) data listing including but not limited to verbatim term, preferred term, system organ class, CTCAE grade, and relationship to study treatment will be provided. Deaths, other SAEs, and other significant AEs, including those leading to discontinuation of study treatments, will be listed.

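### TEAE set (iii) pools placebo subjects newly starting pexidartinib with subjects already about 24 weeks into it, and sets (iii) and (iv) give only crude percentages over open-ended follow-up

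*Combined protocol and SAP*

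**What the plan says.** Section 7.10 summarizes TEAEs for four data sets:

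- (i) "Part 1 data for the subjects who received blinded pexidartinib in Part 1";
- (ii) the matching Part 1 data for blinded placebo;
- (iii) "All data from open-label pexidartinib treatment, ie, Part 2 data from all subjects", with no split by Part 1 arm;
- (iv) "Aggregate pexidartinib data, ie, data from Parts 1 and 2 for the subjects who received pexidartinib in Parts 1 and 2", to which the Part 2 data of former placebo subjects are added.

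Under Section 7.10.1, counts and percentages of subjects with TEAEs "will be tabulated by the worst CTCAE grade, SOC, and PT, with a breakdown by data set". Serious TEAEs and TEAEs leading to discontinuation are handled in the same way. Neither section plans a person-time rate, a time window or a time-to-onset analysis. The TEAE clock starts at study treatment, not at pexidartinib: "TEAEs are AEs that occur, having been absent before the first dose of study treatment".

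On who enters Part 2, Section 3.1 says: "Those subjects who complete Part 1 (ie, complete 24 weeks of dosing and the Week 25 assessments) will be eligible to advance to Part 2". Placebo subjects were included until 30 Sep 2016. Section 3.3 says that the length of Part 2 differs between subjects. On timing of liver injury, the hepatic safety update of December 2017 in the introduction says: "Cases of cholestasis have been observed in the first 8 weeks". Section 2.1 lists long-term safety among the objectives.

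**The concern.** A pooled percentage is useful when the people pooled face roughly the same risk for roughly the same time. Set (iii) meets neither condition. A former placebo subject enters Part 2 at day 1 of exposure. A subject from the pexidartinib arm generally enters after 24 weeks on the drug, having been selected for tolerating it. If an adverse effect clusters in the first weeks, nearly all of that risk sits in the first group, while the second group fills the denominator.

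Follow-up is a separate matter. Sets (i) and (ii) cover about 24 weeks. Sets (iii) and (iv) run for as long as each subject stays. A crude percentage for an event that can happen at any time rises with follow-up even when the underlying risk does not change.

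This matters because, under Section 3.1, the end-of-trial update is a descriptive analysis of Part 2 data only, and set (iii) is the TEAE set defined on exactly those data. The protocol already recognizes the issue for efficacy: Section 7.6.2 keeps former placebo subjects apart as Group C when summarizing duration of response, with their own Part 2 baseline. The TEAE sets do not separate them.

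**Working it through.** The plan gives no TEAE incidence by data set, so there is no figure of its own to reproduce. The values below are assumptions, shown over a range. The documents do not state how many subjects crossed over; as planned, it is at most the 63 placebo subjects in Section 7.12.

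**1. Pooling in set (iii).** Let c be the crossover share of set (iii), e the risk of an early event on first exposure, and r the relative risk in subjects already past 24 weeks.

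Pooled percentage = c·e + (1 − c)·r·e, so pooled ÷ first-exposure risk = c + (1 − c)·r.

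| c | r | ratio | pooled figure if e = 10% |
|---|---|---|---|
| 0.2 | 0 | 0.20 | 2.0% |
| 0.2 | 0.25 | 0.2 + 0.8 × 0.25 = 0.40 | 4.0% |
| 0.5 | 0 | 0.50 | 5.0% |
| 0.5 | 0.25 | 0.5 + 0.5 × 0.25 = 0.625 | 6.25% |

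A crossover-only row would show 10% in every line. The pooled figure also misstates continued risk. With r = 0.25 it is 0.40 ÷ 0.25 = 1.6 times that risk at c = 0.2, and 0.625 ÷ 0.25 = 2.5 times at c = 0.5.

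**2. Unequal follow-up, for late or continuing events.** Take a constant hazard of 0.002 per week, which is 0.002 × 5218 = 10.4 per 100 person-years (52.18 weeks per year). Crude percentage = 1 − exp(−0.002·t):

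- t = 24 weeks: 4.7%
- t = 48 weeks: 9.2%
- t = 96 weeks: 17.5%
- t = 144 weeks: 25.0%

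The hazard is the same throughout; only the length of observation differs.

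**3. Why one overall exposure-adjusted rate is not the remedy.** Suppose a 10% risk falls entirely in the first 8 weeks. The hazard there is −ln(0.9) ÷ 8 = 0.01317 per week, and zero afterwards. Person-time to first event is 0.1 ÷ 0.01317 = 7.59 weeks in the first 8 weeks, plus 0.9 for each later week of follow-up.

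- All followed 24 weeks: 7.59 + 0.9 × 16 = 21.99 weeks, and 0.10 × 5218 ÷ 21.99 = 23.7 per 100 person-years.
- Equal mix of 24, 48, 96 and 144 weeks: mean later time is (16 + 40 + 88 + 136) ÷ 4 = 70 weeks, so 7.59 + 0.9 × 70 = 70.59 weeks, and 0.10 × 5218 ÷ 70.59 = 7.4 per 100 person-years.

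Counted from first pexidartinib dose, the crude percentage stays at 10% in both cases, while the single rate falls by more than two thirds. A rate confined to weeks 1–8 would be 0.01317 × 5218 = 68.7 per 100 person-years in both.

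**The case against.** A reader might infer that the plan as a whole dilutes or hides early liver toxicity. The documents do not support that. Sets (i) and (ii) show first exposure over 24 blinded weeks against concurrent randomized placebo, and so cover the first 8 weeks in full. Set (iv), on its natural reading, counts former placebo subjects from their first pexidartinib dose, so an event confined to the first weeks is not diluted there. Section 7.10.2 summarizes laboratory results by visit, treatment group and study part, adds grade shift tables, and lists Grade 3 or 4 results. Serious events and events leading to withdrawal are listed by subject, and Section 7.5 summarizes exposure. No hypothesis test rests on set (iii). All of this stands, and it limits the point to what sets (iii) and (iv) can show.

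It does not remove the point. Set (i) cannot stand in for a crossover row, because Part 1 opened at 1000 mg/d for two weeks whereas Part 2 opens at no more than 800 mg/d. Set (i) says nothing about risk after 24 weeks. Set (iv) is again a crude percentage over unequal follow-up. Laboratory summaries do not replace incidence of TEAEs, serious events or discontinuations, and Section 7.10.2 does not make clear whether treatment group separates crossovers within Part 2.

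Section 7.4 sends further details to a SAP, and no separate SAP text is in the document reviewed, so extra tables could be specified there. Section 7.10 nevertheless fixes the four sets itself and does not defer this choice.

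**Conclusion.** The point holds for sets (iii) and (iv). The set (iii) percentage is a mixture that estimates neither first-exposure nor continued-exposure risk. Rates of late or continuing events in sets (iii) and (iv) cannot be compared with those in sets (i) and (ii).

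The direction of the dilution follows from the set definition together with the early timing of cholestasis. Its size does not, because crossover share and relative risk are assumed. Over the range examined the pooled figure is between one fifth and five eighths of first-exposure risk, so a statement such as less than half would not hold throughout. The pooling is also bounded, since crossover ended on 30 Sep 2016. This is a cheap improvement to descriptive safety tables; it does not touch the randomized safety comparison.

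**What to change.** In Section 7.10, report set (iii) separately for subjects from Part 1 pexidartinib and from Part 1 placebo. For sets (iii) and (iv), tabulate TEAEs, serious TEAEs and TEAEs leading to discontinuation by time since first pexidartinib dose, for example weeks 1–8, 9–24 and after 24. Give the number at risk at the start of each window, and confidence intervals. State that the clock for former placebo subjects starts at their first Part 2 dose, because the current TEAE reference point is their first placebo dose. Give exposure-adjusted rates only within these windows, not as one overall rate.

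The cost is a little more programming; event and dosing dates are already collected. Crossover-only rows will rest on few subjects. At an assumed true risk of 3%, the chance of seeing at least one case, 1 − 0.97^n, is 37% with 15 crossovers, 60% with 30 and 85% with 63. An empty cell must therefore be read with its interval.

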7.10.1. Analysis of Treatment-emergent Adverse Events

TEAEs are AEs that occur, having been absent before the first dose of study treatment, or have worsened in severity after the initiating the study treatment. TEAEs will be coded using MedDRA and assigned grades based on version 4.0 of the National Cancer Institute's Common Terminology Criteria for Adverse Events (NCI CTCAE). The number and percentage of subjects reporting TEAEs will be tabulated by the worst CTCAE grade, SOC, and PT, with a breakdown by data set (Section 7.10). Similarly, the number and percentage of subjects reporting treatment-emergent SAEs will be tabulated, as well as TEAEs leading to discontinuation of study treatments.

A by-subject AE (including treatment-emergent) data listing including but not limited to verbatim term, preferred term, system organ class, CTCAE grade, and relationship to study treatment will be provided. Deaths, other SAEs, and other significant AEs, including those leading to discontinuation of study treatments, will be listed.

7.10.2. Clinical Laboratory Evaluation Analyses

Descriptive statistics will be provided for the clinical laboratory results by scheduled time of evaluation and by treatment group and study part for the Safety Analysis Set, as well as for the change from baseline. The baseline value is defined as the last non-missing value before the initial administration of study treatment. In addition, mean change from baseline will be summarized for the maximum and minimum post-treatment values and the values at the End of Treatment visit.

Abnormal clinical laboratory results will be graded according to NCI CTCAE version 4.0, if applicable, and the grade will be presented in a by-subject data listing. A shift table, presenting by treatment group the 2-way frequency tabulation for baseline and the worst post-treatment value according to the NCI CTCAE grade, will be provided for clinical laboratory tests. Abnormal clinical laboratory test results deemed of clinical significance or of Grade 3 or 4 will be listed.

7.10.3. Vital Sign Analyses

Descriptive statistics will be provided for the vital signs measurements by scheduled time of evaluation and by treatment group and study part for the Safety Analysis Set, as well as for the

change from baseline. The baseline value is defined as the last non-missing value before the initial administration of study treatment. In addition, mean change from baseline will be presented by treatment group for the maximum and minimum post-treatment values and the values at the End of Treatment visit.

7.10.4. Electrocardiogram Analyses

Descriptive statistics will be provided for the ECG measurements by scheduled time of evaluation and by treatment group for the Safety Analysis Set, as well as for the change from baseline. The baseline value is defined as the last non-missing value before the initial administration of study treatment. In addition, the number and percentage of subjects with ECG interval values meeting the criteria will be tabulated (eg, QTc \leq 450 ms, $>$ 450 to \leq 480 ms, $>$ 480 ms to \leq 500 ms, and $>$ 500 ms) and QTcF maximum changes from baseline ($>$ 30 and $>$ 60 ms) over all post-treatment evaluations will be summarized. ECG data will also be presented in the data listings.

7.10.5. Echocardiogram Analyses

Ejection fraction data will be summarized descriptively, for the Safety Analysis Set, including values at baseline and each time point along with mean change from baseline.

7.10.6. Analysis of Physical Examination Findings

Physical examination data will be listed.

7.10.7. Concomitant Medication Analyses

Concomitant medications will be coded using the World Health Organization drug dictionary (most recent version). Number and percentage of subjects taking concomitant medications will be summarized for the Safety Analysis Set by treatment group.

7.11. Data Monitoring Committee

An independent DMC will be responsible for safeguarding the interests of study subjects, assessing the safety of the interventions during the trial, and monitoring the overall conduct of the trial. The DMC will also make recommendations about continuing, modifying, or stopping the trial. To enhance the integrity of the study, the DMC may also formulate recommendations relating to subject selection, recruitment, and management, improving adherence to protocol-specified regimens and subject retention, and data management and quality control procedures.

A separate DMC Charter will define the DMC membership, its roles and responsibilities, and the process for providing feedback to the Sponsor.

7.12. Sample Size Determination

For the purpose of sample size evaluation, the assumed rates of responders (subjects achieving a CR or PR) for the primary endpoint are 10% (placebo) and 35% (pexidartinib), respectively. Based on the use of a 2-sided, two-sample comparison of proportions at the $\alpha=0.05$ level of significance by Fisher's exact test, a sample size of 126 ITT randomized subjects (63 per arm)

provides 90% power to detect this magnitude of difference. The sample size was calculated using nQuery Advisor 7.0 with the module of two-group Fisher's exact test of equal proportions.

8. ETHICAL CONSIDERATIONS

This study will be conducted in accordance with ethical principles founded in the Declaration of Helsinki and in compliance with the protocol, GCP, and applicable regulatory requirements (including International Conference on Harmonisation [ICH] guidelines). The IRB/IEC will review all appropriate study documentation in order to safeguard the rights, safety and well-being of the subjects. The study will only be conducted at sites where IRB/IEC approval has been obtained. The protocol, IB, informed consent form, advertisements (if applicable), written information given to the subjects (including diary cards and PRO instruments), safety updates, annual progress reports, and any revisions to these documents will be provided to the IRB/IEC by the Investigator or the Sponsor, as allowable by local regulations.

9. SAFETY ASSESSMENT

9.1. Reporting Adverse Events and Serious Adverse Events

All AEs occurring after the subject signs the informed consent form and through the Post-Treatment Visit (28 ± 7 days after the last dose of study treatment), whether observed by the Investigator or reported by the subject, will be recorded on the AE eCRF page. Medical conditions (including laboratory values/vital signs that are out of range) that were diagnosed or known to exist prior to informed consent will be recorded as part of medical history. All SAEs are to be reported according to the procedures in Section 9.3 (SAE Reporting-Procedure for Investigators).

Always report diagnosis as the AE or SAE term(s). When a diagnosis is unavailable, report the primary sign or symptom as the AE or SAE term with additional details included in the narrative until the diagnosis becomes available.

If the signs and symptoms are distinct and do not suggest a common diagnosis, report them as individual entries of AE or SAE. For events that are serious due to hospitalization, the reason for hospitalization must be reported as the SAE (diagnosis or symptom requiring hospitalization). A procedure is not an AE or SAE, but the reason for the procedure may be an AE or SAE. Pre-planned (prior to signing the informed consent form) procedure or treatment requiring hospitalization for pre-existing conditions that do not worsen in severity should not be reported as SAEs (see Section 9.2 for definitions). For deaths, the underlying or immediate cause of death should always be reported as an SAE. Disease progression is a study endpoint and, consequently, should not be reported as an AE/SAE. However, when a subject dies from disease progression with no other immediate causes, "disease progression" should be reported as an SAE. In addition, any serious untoward event that may occur subsequent to the reporting period that the Investigator assesses as related to study treatment should also be reported and managed as an SAE.

At each visit, the Investigator will determine whether any AEs have occurred by evaluating the subject. Adverse events may be directly observed, reported spontaneously by the subject or by questioning the subject at each study visit. Subjects should be questioned in a general way, without asking about the occurrence of any specific symptoms. The Investigator must assess all AEs to determine seriousness, severity, and causality, in accordance with the definitions in Section 9.2. The Investigator's assessment must be clearly documented in the site's source documentation with the Investigator's signature. All laboratory values must be appraised by the Investigator as to clinical significance. All abnormal laboratory values considered clinically significant by the Investigator must be recorded as an adverse event on the eCRF, and if serious, report as an SAE following the procedures in Section 9.3.

The Investigator should follow subjects with AEs until the event has resolved or the condition has stabilized. In case of unresolved AEs, including significant abnormal laboratory values at the end of study assessment, these events will be followed up until resolution or until they become clinically not relevant.

9.2. Definitions

9.2.1. Adverse Event

An AE is any untoward medical occurrence in a subject or clinical investigation subject administered a pharmaceutical product and which does not necessarily have to have a causal relationship with this treatment. An AE can therefore be any unfavorable and unintended sign (including an abnormal laboratory finding, for example), symptom, or disease temporally associated with the use of a medicinal product, whether or not considered related to the medicinal product.³⁶

It is the responsibility of Investigators, based on their knowledge and experience, to determine those circumstances or abnormal laboratory findings that should be considered AEs.

